CASE
COMPREHENSIVE
CANCER CENTER

A Cancer Center Designated by the
National Cancer Institute

STUDY NUMBER: CASE 5217

ClinicalTrials.gov NCT #: NCT03335813

Protocol Date: 22 November 2017

STUDY TITLE: Endoesophageal Brachytherapy for Patients with Esophageal Cancer:
A Balloon Repositioning, Multichannel Radiation Applicator for
Optimizing Treatment Delivery (IRB# IP 30)

PRINCIPAL INVESTIGATOR: [name]
Case Comprehensive Cancer Center
Cleveland Clinic Florida
Maroone Cancer Center
[name]
[name]
[contact]
[contact]

SUB-INVESTIGATORS: [name]
Case Comprehensive Cancer Center
Cleveland Clinic Florida
Maroone Cancer Center
[name]
[name]
[contact]
[contact]

[name].
Case Comprehensive Cancer Center
Cleveland Clinic
[name]
[name]
[contact]
[contact]

STUDY COORDINATOR:

[name]
Case Comprehensive Cancer Center
Cleveland Clinic Florida
Maroone Cancer Center
[name]
[name]
[contact]
[contact]

SPONSOR:

Case Comprehensive Cancer Center
Cleveland Clinic - Innovative Practice Group

SUPPORT/FUNDING:

Cleveland Clinic

SUPPLIED AGENT(S):

N/A

IND #:

N/A

[figure not shown]
OTHER AGENT(S):

N/A

SUMMARY OF CHANGES

Please provide a list of changes from the previous approved version of the protocol starting at IRB approval. This table will remain blank until initial IRB approval. The list shall be a brief overview. When appropriate, a brief justification for the change should be included. This is a running list for the life of the study.

STUDY SCHEMA

PROTOCOL SUMMARY

Protocol Number/Title	CASE 5217
Study Phase	PILOT TRIAL
Brief Background/Rationale	This innovative study will be an improvement over our previously designed 3-tube endoesophageal brachytherapy technique in patients who are candidates for esophageal brachytherapy. The brachytherapy planning process will utilize our multichannel balloon applicator as described within.
Primary Objective	Pilot study of multichannel endoesophageal brachytherapy applicator to determine dose distribution and conformality of a 6 channel balloon repositioning applicator.
Secondary Objective(s)	
1. To compare conformality and normal tissue doses versus previous 3-tube design.2. To evaluate acute toxicity of multichannel endoesophageal brachytherapy applicator.
Exploratory Objective(s)	None
Correlative Objective(s)	None
Sample Size	Number expected to accrue: 5 Age: ≥ 18 Gender: Male and Female
Disease sites/Conditions	Esophagus / Esophageal Cancer
Interventions	Agent/Route: Endoesophageal Brachytherapy Cycle Length: Weekly Number of cycles: Between 3 and 6 cycles

ABBREVIATIONS

CCCC	Case Comprehensive Cancer Center
CRF	Case Report Form
DCRU	Dahm's Clinical Research Unit
DSTC	Data Safety and Toxicity Committee
FDA	Food and Drug Administration
ICF	Informed Consent Form
IRB	Institutional Review Board
PRMC	Protocol Review and Monitoring Committee
SOC	Standard of Care
CCF	Cleveland Clinic Foundation
UH	University Hospitals
IPC	Innovative Practice Committee

TABLE OF CONTENTS

1.0 INTRODUCTION

Esophageal cancer is a global health problem with over 400,000 new cases and a similar number of deaths occurring each year.¹ Although the highest incidence rates are observed in Southern and Eastern Africa and Eastern Asia, 16,980 cases are diagnosed each year in the United States and 15,590 deaths are attributed to this cancer annually.² Depending on a combination of patient factors and disease characteristics, patients are often treated with definitive chemoradiation therapy or surgical resection, with or without pre-operative chemoradiation therapy. For patients treated with a non-operative approach, phase III trials using concurrent chemoradiation therapy have revealed high local failure rates (crude local failure 45-55%) in patients receiving moderate radiation therapy doses (50 Gy).^{3,4} Even in patients undergoing dose escalation (64 Gy) using external beam radiation therapy, the local failure rate continues to be problematic (crude: 50%, 2 year actuarial: 56%).⁴ Unfortunately, the nearby organs at risk (such as the lungs, heart, and spinal cord) limit the amount of radiation therapy that can be delivered via standard external beam radiation therapy techniques.

1.1 Background

Brachytherapy is a radiation therapy treatment technique that allows for high doses of radiation to be delivered directly to the tumor volume while sparing the surrounding normal structures. Specifically, high-dose-rate (HDR) brachytherapy delivered using modern devices allows for high doses of radiation to be delivered directly to the tumor in a short period of time (minutes). In an effort to intensify therapy, multiple institutions investigated the role of esophageal brachytherapy in nonoperable patients. For example, Tamaki and colleagues demonstrated a local control rate of 79% at 5 years for 54 patients undergoing external beam radiation therapy followed by a 2-3 fraction brachytherapy boost.⁵ Although some investigators such as Tamaki reported encouraging results, the concern with this approach was the high incidence of treatment-related toxicity.

A prospective Radiation Therapy Oncology Group (RTOG) trial was subsequently performed in patients undergoing definitive concurrent chemoradiation therapy for non-metastatic esophageal cancer.⁶ Patients were treated to a dose of 50 Gy with concurrent chemotherapy, a two week break, and then three fractions of HDR brachytherapy at weekly intervals to a dose of 15 Gy (5 Gy per fraction per week). The brachytherapy applicator was prescribed to treat the tumor volume plus a one-centimeter margin proximally and distally. The dose was prescribed to a one cm depth from the source axis. Unfortunately, the high treatment-related toxicity (1-year actuarial fistula rate: 18%) observed with this approach limited its routine use and led to the development of strict selection criteria for patients to be treated with brachytherapy by the American Brachytherapy Society (ABS).⁷ According to the consensus guidelines, good candidates for the procedure as a boost to definitive treatment include those with a unifocal thoracic esophageal cancer ≤ 10 cm in length with no extraesophageal extension of disease, and no nodal or metastatic disease. Strict contraindications for esophageal brachytherapy included patients with an esophageal fistula, cervical esophageal location, or a stenosis that could not be bypassed during endoscopy.

In addition to nonoperable patients with esophageal cancer undergoing definitive therapy, patients with recurrent or metastatic disease may symptomatically benefit from HDR brachytherapy. In fact, a randomized controlled trial was recently performed in 209

patients with dysphagia from inoperable esophageal or gastroesophageal junction cancer treated with stent placement or a single dose (12 Gy) brachytherapy application. This trial showed a higher incidence of complications in patients undergoing stent placement (33% vs. 21%, $p=0.02$) with an improvement in quality-of-life and better long-term relief of dysphagia in patients undergoing brachytherapy.⁸ Therefore, patients with unresectable local disease progression, thoracic esophagus lesions with distant metastasis, or those who recurred after definitive external beam radiation therapy can also be considered candidates for the procedure per the ABS guidelines.⁷ In addition to these criteria, reported institutional series support the use of HDR brachytherapy in patients with symptomatic stenosis, dysphagia, or tumor hemorrhage as an alternative to endoscopy with coagulation or stent placement.⁹

1.2 Preclinical Data

As previously mentioned, one of the limitations of esophageal brachytherapy is the lack of the treating physician's ability to modulate the dose when using a single tube device. The currently utilized and innovative approach used in our department is a 3-tube technique. Use of the 3-tube technique improves the dose homogeneity and reduces the doses to heart, lungs, bronchus, trachea, and vertebral bodies.

[figure not shown]

Figure 1. Bar graphs demonstrating the improved dose homogeneity with the 3-tube approach. V100, V150, V200, and V300 represent the volume receiving 100%, 150%, 200%, and 300% of the prescribed dose, respectively.

[figure not shown]

Figure 2. Bar graphs demonstrating the reduced maximum doses of radiation to the nearby critical structures when utilizing a 3-tube technique compared to a single tube technique.

As can be seen in Figure 3, with dose delivery using a single lumen (left picture), there are increased doses delivered to the surrounding normal structures. With use of the three-tube technique (right), the prescription doses can be shaped to match the tumor volume more accurately.

[figure not shown]

Figure 3. Axial CT treatment planning images for two patients undergoing HDR brachytherapy. Image on the left demonstrates the isodose distribution in a patient treated with a single tube, patient on right was treated with 3-tube technique. Note that all of the circles (representing isodose lines) are smaller with the 3-tube technique.

[figure not shown]

Figure 4. Axial (A), sagittal (B), and coronal (C) CT treatment planning images for a patient with a locally advanced esophageal cancer undergoing HDR brachytherapy. Two transesophageal tubes (each 1.0 meter length) were used to deliver a dose of 5 Gy

1.3 Clinical Data to Date

In an effort to further improve on our treatment technique, we have made substantial improvements by creating a novel balloon repositioning, multichannel brachytherapy applicator itself (i.e., 6 channels instead of 3-tubes). The following figures illustrate the current prototype of the new device designed specifically for this procedure. This new device contains a therapeutic balloon with a maximum diameter of 20 mm when inflated and an anchor balloon with a maximum diameter of 24 mm when inflated. A semi-hard tip was added to the end of the applicator tapering from the 10 mm diameter of the tube to 4-5 mm in diameter at the distal end to allow for easier placement through a narrow, stenotic tumor or strictured area, along with a guidewire channel added to the semi-hard tip. Finally, the seed channels have been designed to extend along the applicator and terminate at the midpoint of the anchor balloon to allow the inflated anchor balloon to push the seed channels closer to the gastroesophageal junction wall (closer to the tumor to improve dose delivery).

A previous prototype incorporating many of the above improvements was tested in a porcine model which showed ease of placement of the device and successful anchoring at the gastroesophageal junction.

Figure 5. Overview of the catheter with inflated balloons.

[figure not shown]

Figure 6. View of seed delivery channels (A) and cross-view (B)

[figure not shown]

Figure 7. Partial views of the catheter

[figure not shown]

Figure 8.Deflated applicator (without outer sheath)

1.4 Rationale

Although patient access to endoscopy centers has expanded and the incidence of esophageal cancer continues to increase, one of the key limiting factors in the more widespread use of esophageal brachytherapy is the limitations of the current single catheter approach. Therefore, in an effort to improve on this technique, patients in our department have been treated using a novel 3-tube technique. This 3-tube technique makes the dose more conformal and reduces the "hot spots" of radiation (doses above the prescription dose) in the esophageal wall. We evaluated the clinical outcomes of the initial thirteen patients treated for medically unresectable, stage 0-IVA, esophageal cancer with our 3-tube design: Five patients were treated with HDR brachytherapy alone and eight were treated with a combination of HDR brachytherapy and external beam radiation therapy. Across all patients, the 18-month local control, disease-free-survival, and overall survival rates were 81%, 74%, and 92%, respectively. Moreover, no patients have suffered a fistula as a result of treatment and only two patients have required dilation for esophageal strictures. A majority of the patients (11 of 13) continue to be free of dysphagia at a median of 17 months of follow-up. These promising initial results have fueled our interest in further innovation of our delivery technique in an effort to broaden the utility of esophageal brachytherapy as well as provide more effect cancer-directed therapy while maintaining a patient's quality of life.

2.0 OBJECTIVES

2.1 Primary Objective

Pilot study of multichannel endoesophageal brachytherapy applicator to determine dose distribution and conformality of a 6 channel balloon repositioning applicator.

2.2 Secondary Objective(s)

- a.** To collect data in order to show how the 6-tube endoesophageal brachytherapy technique will be an improvement (more conformed dose distribution) over our previously designed 3-tube endoesophageal brachytherapy technique in patients who are candidates for esophageal brachytherapy
- b.** To evaluate acute toxicity of novel endoesophageal brachytherapy applicator.

3.0 STUDY DESIGN

This innovative study will be an improvement over our previously designed 3-tube endoesophageal brachytherapy technique in patients who are candidates for esophageal brachytherapy. The brachytherapy planning process will utilize our multichannel balloon applicator as described above.

Intraoperative procedure

In the operating room, the patient's pulse, pulse oximetry, and blood pressure are obtained prior to the procedure and during the procedure. The patient is typically medicated with Demerol (100 mg IV) and Versed (4 mg IV) throughout the procedure and Benzocaine topically prior to the procedure as per standard anesthesia practices for esophageal brachytherapy patients. The endoscope is passed through the mouth under direct visualization and advanced distally, typically to the stomach or 2nd portion of the duodenum. The scope is then gradually withdrawn and the mucosa is examined. Of note, if a significant area of stenosis is identified, this is dilated to allow for a sufficient diameter for insertion of the brachytherapy applicator. Once the cancerous mucosa is visualized, radio-opaque markers (endoclips or metallic seeds) are placed with ~2 cm margins on the proximal and distal ends of the tumor. A guidewire is then passed to the stomach and the endoscope is removed. Over the guidewire, the brachytherapy applicator device is then placed under fluoroscopic guidance ensuring that the distal end travels past the most distal radio-opaque endoclip and typically into the stomach. The brachytherapy applicator is then stabilized and secured by inflating the anchor balloon and/or fixing to the mouth guard after removal of the guidewire.

After applicator placement, the patient is transported to the Department of Radiation Oncology for a CT simulation. Metal dummy seeds are placed into the channels. The treatment balloon is inflated to move the channels in close proximity to the esophageal tumor. The patient is placed in the supine position and undergoes a planning CT scan of the neck and thorax. The CT images are downloaded into the Oncentra treatment planning system and then tumor volume as well as normal critical structures are outlined by the treating radiation oncologist. During the treatment planning phase, the patient is transported to the nursing unit for observation. Following completion of treatment planning, the patient is transported to the HDR brachytherapy treatment room and maintained on the transport cart in the supine position. The exterior portions of the brachytherapy channels are connected to the remote afterloader HDR device. AnIridium-192 seed will enter the channels to deliver the planned course of brachytherapy. After treatment delivery, the brachytherapy channels are disconnected from the HDR afterloader device. After deflation of the anchor and treatment balloons and disconnection from the mouthpiece the multichannel applicator is removed gently from the patient. No devices will remain in the patient. The patient is subsequently transported to the nursing unit for vital sign monitoring for approximately one-half hour prior to discharge to home.

Radiation therapy treatment planning

Patients will be planned using our standard 3D, CT-based, Oncentra treatment planning system. The target volume will be identified during endoscopy and an approximately 2 cm proximal and distal margin will be added to account for microscopic tumor extension (beyond the gross macroscopic disease) and to account for any spatial inaccuracy of the applicator device positioning. The dose will be prescribed to treat the target volume with modification if necessary to decrease doses to the normal surrounding tissues.

[figure not shown]

Figure 9. Diagram demonstrating the treatment volume for a 4 cm esophageal tumor treated with a HDR brachytherapy applicator. A 2 cm margin is added on either end to account for microscopic tumor extension and to account for any spatial inaccuracy of the applicator device positioning.⁹

Patients will be treated using standard radiation therapy dosing guidelines, typically in 2-6 sessions separated by weekly intervals. In addition to identifying the treatment volume (CTV, PTV), the organs at risk will be identified. Typical dosimetry constraints, such as the dose delivered to 90% of the tumor volume (D90) and the volume of the tumor receiving the prescription dose (V100) will be reviewed to ensure that an acceptable treatment plan is designed. The use of our new applicator will improve the dose homogeneity as well as lower the dose to the nearby normal organs.

Data Collection:

The focus of the data collection includes but is not exclusive (or limited) to:

- A. Date of the procedure
- B. Radiation therapy dosimetry and treatment planning parameters
- C. Patient tumor characteristics
- D. Video of the endoscopy procedure
- E. All CT imaging datasets acquired for patient treatment
- F. Screen shots from the treatment plan
- G. Comments and feedback from members of the treatment team
- H. Acute toxicity

Data Collection (cont'd)

- I. Tumor Response: CR, PR, SD, PD
- J. Esophageal Ulceration (Yes / No)
- K. Esophageal Fistula (Yes / No)
- L. Esophageal Stricture (Yes / No)
- M. Need for Dilation (Yes / No)

Data Analysis:

As this application is specifically for a new device to deliver the same doses of radiation therapy previous administered using single or multi-tube approaches, we will analyze data on patient outcome and dosimetry data in comparison with our historical controls. Specifically, we will use endoscopic follow-up images and correlate the visual changes with the radiation therapy doses delivered to the tumor, esophageal wall, and nearby organs at risk.

3.1 Study design / cohorts

There is only one cohort for this trial. Subjects will be eligible based on meeting the inclusion/exclusion criteria.

3.2 Number of Subjects

Approximately 5 subjects will be enrolled in this trial.

3.3 Replacement of Subjects

If subject does not receive the esophageal brachytherapy treatment, they will be excluded from the trial and another subject will be selected.

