5.0 REGISTRATION

All subjects who have been consented are to be registered in the OnCore™ Database. For those subjects who are consented, but not enrolled, the reason for exclusion must be recorded.

All subjects will be registered through Cleveland Clinic Florida's Maroone Cancer Center and will be provided a study number by contacting [name] at [contact] or [contact].

Eligible subjects will be enrolled into the trial and treated as per standard of care.

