6.8 Duration of Follow Up

Subjects will be followed for 6 months after the initial procedure or until death, whichever occurs first.

The clinical course of each event will be followed until resolution, stabilization, or until it has been determined that the study treatment or participation is not the cause.

Serious adverse events that are still ongoing at the end of the study period will necessitate follow-up to determine the final outcome. Any serious adverse event that occurs after the study period and is considered to be possibly related to the study treatment or study participation will be recorded and reported immediately.

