8.3.3 Adverse Event Evaluation

The investigator or designee is responsible for ensuring that all adverse events (both serious and non-serious) observed by the clinical team or reported by the subject which occur after the subject has signed the informed consent are fully recorded in the subject’s medical records. Source documentation must be available to support all adverse events.

A laboratory test abnormality considered clinically relevant (e.g., causing the subject to withdraw from the study, requiring treatment or causing apparent clinical manifestations, result in a delay or dose modification of study treatment, or judged relevant by the investigator), should be reported as an adverse event.

The investigator or sub-investigator (treating physician if applicable) will provide the following for all adverse events (both serious and non-serious):

- Event term (as per CTCAE)
- Description of the event
- Date of onset and resolution
- **Expectedness of the toxicity**
- **Grade of toxicity**
- **Attribution of relatedness to the investigational therapy/agent- (this must be assigned by an investigator, sub-investigator, or treating physician)**
- Action taken as a result of the event, including but not limited to; no changes, dose interrupted, reduced, discontinued, etc. or action taken with regard to the event, i.e. no action, received conmed or other intervention, etc.
- Outcome of event

Descriptions and **grading scales** found in the NCI Common Terminology Criteria for Adverse Events (CTCAE) version **4.0** will be utilized for agent AE reporting.

An expected adverse event is an event previously known or anticipated to result from participation in the research study or any underlying disease, disorder, or condition of the subject. The event is usually listed in the Investigator Brochure, consent form or research protocol.

An unexpected adverse event is an adverse event not previously known or anticipated to result from the research study or any underlying disease, disorder, or condition of the subject.

Attribution is the relationship between an adverse event or serious adverse event and the study drug. Attribution will be assigned as follows:

- Definite – The AE is clearly related to the study drug.
- Probable – The AE is likely related to the study drug.
- Possible – The AE may be related to the study drug.
- Unlikely – The AE is doubtfully related to the study drug.
- Unrelated – The AE is clearly NOT related to the study drug.

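### Section 3.3 removes and replaces any never-treated patient and no safety set is defined, so harm from a pre-dose insertion attempt could be left out of the reported applicator toxicity

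*Combined protocol and SAP*

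**What the plan says.** The replacement rule in Section 3.3 is one sentence: "If subject does not receive the esophageal brachytherapy treatment, they will be excluded from the trial and another subject will be selected". It makes no exception for a patient in whom the applicator was tried, and it is not confined to any particular analysis.

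The second secondary objective in Section 2.2 is "To evaluate acute toxicity of novel endoesophageal brachytherapy applicator". It concerns the device, not only the radiation dose.

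Section 3.0 (repeated in Section 6.1) sets out what happens before any dose. The patient is sedated and endoscoped, and "if a significant area of stenosis is identified, this is dilated to allow for a sufficient diameter for insertion of the brachytherapy applicator". Markers, guidewire and applicator are placed and the anchor balloon may be inflated. The treatment balloon is then inflated and a planning CT is taken. Only then does treatment begin: "Following completion of treatment planning, the patient is transported to the HDR brachytherapy treatment room". Section 3.4 likewise puts the first session after the plan has been made.

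Other sections bear on a patient who never reaches a dose:

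- Section 5.0: "All subjects who have been consented are to be registered in the OnCore" database. For those consented but not enrolled, the reason must be noted.
- Section 8.3.3: adverse events "which occur after the subject has signed the informed consent are fully recorded" in the medical record.
- Sections 8.5.1 to 8.7: all serious adverse events go to the lead investigator, OnCore and the Data Safety and Toxicity Committee.
- Section 8.5: the reporting window closes 30 days after the last dose. Its start is still an unfilled template prompt.
- Section 6.8: "Subjects will be followed for 6 months after the initial procedure or until death, whichever occurs first".

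Section 14.0 names no analysis set for toxicity.

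**The concern.** Insertion is part of using a new applicator, and the only placement testing that Section 1.3 reports is of an earlier prototype in pigs. How insertion goes in patients is therefore one of the things this pilot can show.

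The replacement rule is tied to that outcome. An insertion injury bad enough to prevent treatment is itself what triggers Section 3.3, so the patient can be removed because of the kind of harm that objective 2.2b is meant to describe. With about five patients, leaving out one changes the result from some harm to none.

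Replacing untreated patients is sensible for dosimetry, because they have no delivered dose to analyse. The weakness is that Section 3.3 takes them out of the whole trial.

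**Working it through.** **Plan's own figure.** Section 3.2 gives approximately 5 subjects, with no precision target, error rate or formula, so there is nothing to reproduce. The point does not depend on how 5 was chosen.

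**Step 1: can a patient be exposed to the device and still be removed?** Section 3.0 puts endoscopy, dilation, insertion and both balloon inflations before the first dose. Section 3.3 removes anyone with no dose. So yes. A patient who receives at least one session is not removed, and harms at that patient's later insertions still count.

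**Step 2: does another section restore that patient to the toxicity summary?** Sections 5.0, 8.3.3 and 8.5.1 to 8.7 govern registration, recording and expedited reporting. The list of data to be collected in Section 3.0 is open-ended ("The focus of the data collection includes but is not exclusive (or limited) to") and includes acute toxicity. None of these says who is counted under objective 2.2b, and neither does Section 14.0.

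**Step 3: do the follow-up rules agree?** Section 6.8 counts from the initial procedure, a term that is not defined. If it means the first insertion, a patient with an attempt and no dose is removed by Section 3.3 yet followed under Section 6.8. The Section 8.5 window ends relative to the last dose, so for this patient it has no end date.

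**Step 4: effect on the reported proportion.** Suppose five patients are treated without an insertion harm, and one further patient is harmed at insertion and never treated. Clopper-Pearson 95% limits:

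- Removed under Section 3.3: 0/5 = 0%. Upper limit = 1 − 0.025^(1/5) = 0.522. Interval 0 to 52%.
- Counted: 1/6 = 16.7%. Lower limit = 1 − 0.975^(1/6) = 0.004. Upper limit = 0.975 quantile of Beta(2, 5) = 0.641. Interval 0.4 to 64%.

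**Step 5: how likely is such a patient?** The documents give no rate, so these inputs are assumed. Per attempted patient, let q be the chance of being harmed at insertion and never treated, g the chance of going untreated for another reason, and t = 1 − q − g the chance of being treated. If recruitment continues until five are treated, then

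P(at least one such patient) = 1 − [t/(t + q)]^5.

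Example with q = 0.05:

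- g = 0: 1 − 0.95^5 = 0.226.
- g = 0.20: t = 0.75, so 1 − (0.75/0.80)^5 = 0.276.

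| Assumed q | g = 0 | g = 0.20 |
|---|---|---|
| 1% | 4.9% | 6.1% |
| 2% | 9.6% | 11.9% |
| 5% | 22.6% | 27.6% |
| 10% | 41.0% | 48.7% |

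**The case against.** The strongest reply is that the consequence is inferred. Section 3.3 is about replacement and says nothing about toxicity tables. A harm severe enough to stop treatment would probably qualify as serious under Section 8.3.2. It would then reach the lead investigator within 24 hours, OnCore and the safety committee. Sections 6.8 and 8.5 also require an event that has occurred to be followed to resolution or stabilization, whatever the window says. This stands: such events are not lost from the records, and the concern does not say they are. But recording an event does not decide whether the patient is counted in the summary, and the only sentence that bears on that takes the patient out of the trial.

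A second reply concerns Section 6.8. Section 11.2 treats treatment and procedure as one kind of visit, and Section 3.4 counts from the initial treatment, so the initial procedure may simply mean the first treatment session. That reading is possible and would remove the mismatch. The other reading also has support, because Section 3.0 describes insertion under the heading of the intraoperative procedure. The mismatch is therefore conditional on an undefined term.

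Third, exclusion criterion 4 in Section 4.2 makes a patient ineligible if a stenosis cannot be bypassed or dilated for placement. But the described procedure finds and dilates stenosis at the endoscopy itself, so this can come to light only after exposure has begun. It is fair to add that a harm from endoscopy or dilation alone, before the applicator is introduced, is not plainly applicator toxicity.

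Finally, every q and g is assumed, and the higher probabilities need a high rate of a combined event. That is correct, and the figures are illustrative only.

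**Conclusion.** The concern holds, as a minor point. Section 3.3 as written, with no safety set or toxicity denominator anywhere in the plan, allows an applicator harm before the first dose to fall outside the summary for objective 2.2b.

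For one such patient, the difference is between 0/5 and 1/6. The two intervals overlap widely and no decision rule uses them, so what changes is whether the event is counted. The size rests on two assumptions: recruitment continues until five patients are treated, and the five treated patients have no such harm. The chance of the situation arising, 5% to 41% (6% to 49% if a further 20% go untreated for other reasons), rests entirely on assumed rates of 1% to 10%.

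**What to change.** Reword Section 3.3 along these lines: *Replacement applies to the dosimetry set only. Every patient in whom applicator insertion is attempted stays in the safety set for objective 2.2b.* Define both sets in Section 14.0. State there whether harms of endoscopy or dilation are attributed to the applicator or listed separately.

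Report the number of patients with an attempted insertion, the number never treated, and the reason for each.

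Reconcile Section 3.3 with the follow-up and reporting sections. Define the initial procedure in Section 6.8 and say whether its follow-up applies to never-treated patients. In Section 8.5, give these patients a reporting period that starts at consent, in line with Section 8.3.3, and ends at a time counted from the last attempted insertion.

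The cost is a few sentences of protocol text and short adverse event follow-up of a few untreated patients. The reported safety figures may look less favourable. The number of treated patients and the dosimetry analysis do not change.
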